- 1) Cannabis: Participants will be administered active cannabis (7% THC) during the training session and on 1/2 laboratory session days, and inactive cannabis (0% THC) in the other laboratory session. The most frequently reported adverse experiences associated with cannabis administration are increased appetite, sleepiness, concentration difficulties, dependence, faintness, restlessness, confusion, lightheadedness, loss of coordination, clumsiness, shakiness, dizziness, stomach upset, headache, paleness, flushing, sweating, dry mouth, slurred speech, fatigue, heart pounding, and changes in the pattern of heart beats. Additionally, cannabis use during pregnancy increases the risk for premature birth, low birthweight, neural tube defects, anemia, and stillbirth (Gunn et al., 2016; Varner et al., 2014).

Procedures:

- 1) Virtual Reality Headset: Participants may experience dizziness or discomfort from the virtual reality headset. Motion sickness and pressure applied to the face from the headset may lead to clumsiness, shakiness, dizziness, or stomach upset.
- 2) Quantitative Sensory Testing – thermal pain: the nature of this test is to induce moderate pain and discomfort through the application of a cold stimulus, similar to holding an ice cube. However, the participant controls the amount of pain and amount of time exposed to the painful stimulus by clicking a button on the QST apparatus to indicate their pain threshold, and the designated temperature of 4 degrees Celsius in conjunction with a cut-off time of 3 minutes will ensure that this stimulus does not result in tissue damage.
- 3) Confidentiality: Potential participants divulge information that is sensitive and may have adverse social consequences if released. This would include information released to insurance companies, health care agencies, family members, or made public in any way.

Describe procedures for minimizing risks:

- 1) All participants are fully informed of cannabis' side effects, and because all currently smoke cannabis, these effects should be familiar to them. Regardless, we will assess vital signs (blood pressure and heart rate) after patients smoke cannabis to ensure safety. As the medical director of the marijuana laboratory,

[name] will oversee any medical components of the study. In addition to [name], [name], [name] RN, [name], or one of the Medical Fellows ([name], [name], [name], [name], [name], [name], [name]) will be available in the case of an emergency. Women who are pregnant or breast-feeding will not be eligible for study participation. If a woman becomes pregnant during study participation, she will be discontinued from the study and referred to obstetrical treatment.

- 2) During the Training Session, if a participant indicates any discomfort or nausea from the VR headset, the patient, study PI, and the study physician will make the determination together as to whether or not the patient should be enrolled in the study. If a patient experiences nausea or discomfort during either of the laboratory sessions, they can opt to discontinue their study participation and will be observed until the discomfort passes and they can be discharged. If a patient vomits at any point during the Training or Laboratory Sessions, their participation will be discontinued, and they will be observed by study staff until the sensation passes and they can be discharged.
- 3) The QST computerized program utilizes a temperature of 4 degrees Celsius and a cut-off time of 3 minutes to avoid tissue damage.

Definition and Reporting of Adverse Events:

An adverse event is any untoward medical occurrence associated with the use of a drug in humans, whether or not considered drug related (21 CFR 312.32(a)) and a serious adverse event is an adverse event that, in the view of either the investigator or sponsor, it results in any of the following outcomes: death, a life-threatening adverse event, inpatient hospitalization or prolongation of existing hospitalization, a persistent or significant incapacity or substantial disruption of the ability to conduct normal life functions, or a congenital anomaly/birth defect (21 CFR 312.32(a)). Adverse events will be reported as required in IND safety reporting requirements (21 CFR 312.32).

Methods to Protect Confidentiality

All data records containing identifying information will be kept in locked files and on password-protected computers. Only the principal investigator and other core study staff will have access to identifiable information, which will be maintained on site under lock and key. All computer data is stored without names or other identifiers. Participants will be identified only through a numerical code in all electronic databases. This study will be covered by a Federal Certificate of Confidentiality issued by the Department of Health and Human Services (DHHS).

Direct Benefits to Subjects

There are no direct benefits to research volunteers in the proposed studies. Prior to study acceptance, all volunteers will have an extensive medical and psychiatric work-up. We offer all participants the option of obtaining help to abstain from drug taking. Volunteers understand that they can obtain a referral for drug treatment at any stage of their research participation. We repeat our offer for treatment referral at screening and at discharge from the study. We will attempt to obtain a placement in a drug abuse clinic for those people who indicate a desire for help and will inform all volunteers of our ongoing marijuana-treatment studies conducted within the Division of Substance Abuse.

References

Adams, A. J., Brown, B., Haegerstrom-Portnoy, G., Flom, M. C., Jones, R. T. (1978). Marijuana, alcohol, and combined drug effects on the time course of glare recovery. *Psychopharmacology*, 56(1), 81-86.

Bosker, W. M., Theunissen, E. L., Conen, S., Kuypers, K. P., Jeffery, W. K., Walls, H. C., Kauert, G. F., Toennes, S. W., Moeller, M. R., Ramaekers, J. G. (2012). A placebo-controlled study to assess Standardized Field Sobriety Tests performance during alcohol and cannabis intoxication in heavy cannabis users and accuracy of point of collection testing devices for detecting THC in oral fluid. *Psychopharmacology*, 223(4), 439–446. doi:10.1007/s00213-012-2732-y

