Using 30 healthy cannabis users (15 men, 15 women), this study will be one of the first to assess changes in eye behavior as a function of recent cannabis use within a quantified virtual reality (VR) environment. We will examine the effect of smoked cannabis (7% vs. 0% THC) on individual eye movements, with the goal of defining the utility of the eyes as potential objective indicators of cannabis use and intoxication. Four eye tests (nystagmus, smooth pursuit, convergence, and pupillary light response; outlined below), which previous literature has defined as effective in detecting recent drug use (including opioids and alcohol; Murillo et al. 2004), have been compiled into a 5-minute task battery using a VR headset environment equipped with high frequency infrared eye trackers (the HTC Vive with Pupil Labs Tracking). This 5-minute VR battery of four eye tests will be administered prior to cannabis consumption as a baseline, and then at 0, 15, 30, 45, 60, 75, 90, 105, 120, and 165 min after cannabis, with the goal of comparing baseline values to the ten post-cannabis timepoints to detect changes in eye behavior as a function of cannabis intoxication. We will also administer a battery of subjective-effects and mood visual analogue scales (0-100 mm; e.g. 'Good Drug Effect') prior to the eye test battery at each timepoint, allowing us to correlate each outcome of the eye tasks to subjectively reported cannabis impairment and mood.

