In addition to measuring eye behavior as a function of cannabis use, we will utilize the training session of this study to collect exploratory data on the relationship between pupil dilation and experimental pain. There is a small literature suggesting that changes in pupil size can be used as an objective biomarker of pain perception (Wildemeersch, 2018); thus, we would like to collect preliminary data on changes in pupil dilation as a function of pain induction. Using Quantitative Sensory Testing (Medoc TSA-II NeuroSensory Analyzer), we will induce thermal pain threshold and tolerance using a cold stimulus (4.0°C; induced with a 30 x 30 mm Peltier thermode, which is 1.5" square metal applicator that is connected to the TSA-II NeuroSensory Analyzer device and software, and produces an ongoing cold sensation applied to the lower palm of the participant's non-dominant hand). Participants will indicate when they first feel pain (pain threshold), and when the pain becomes too much to bear (pain tolerance) by pressing a button on a controller connected to the TSA-II. As the HTC Vive collects

data on pupil size at a frequency of 120 times per second, throughout exposure to the cold stimulus we will be able to measure and correlate potential changes in pupil size to the patient's subjectively reported pain latencies.

The findings of this study may: 1) characterize the validity of eye tests as an objective measure of cannabis use and intoxication; 2) provide pilot data on the relationship between pupillary changes and pain response.

Background, Significance, and Rationale

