State of the field and current limitations: Previous research on the effects of cannabis on the eyes has been conducted, yet most of this research is decades old and used outdated technology that cannot accurately or frequently measure eye movements and pupil dilation. The literature also presents contradicting results on correlations between cannabis and certain eye movements, specifically regarding nystagmus and smooth pursuit. Despite these studies and the fact that eye movements are currently used in the field to detect drug intoxication, little is known about the causal relationship, if any, between cannabis, eye movements and pupil dilation. To date, no published studies have used modern VR eye trackers and data analysis to build a predictive model of cannabis intoxication. The current study seeks to explore the effects of cannabis on eye movements using a sophisticated eye tracking software to provide an objective, accurate measure of cannabis impairment.

Specific Aims and Hypotheses

Aim 1: Examine the relationship between cannabis intoxication and eye behavior.

Hypotheses: (a) Active cannabis (7% THC) will have an effect on eye behavior, evidenced by lack of convergence, lack of smooth pursuit, presence of nystagmus and pupil dilation when compared to inactive placebo cannabis (0% THC).

Exploratory Aim: Examine the relationship between experimental pain and pupil size.

Hypotheses: (a) Changes in pupil size will correlate with subjective reports of experimental pain threshold and tolerance using Quantitative Sensory Testing thermal pain.

Inclusion/Exclusion Criteria

Description of Subject Population:
Non-treatment seeking cannabis smokers.

CRITERION	METHOD OF ASCERTAINMENT
Inclusion:	
1. Males/non-pregnant females aged 21-55 years	Age verified via identification/Non-pregnancy confirmed via urine toxicology
2. Report smoking cannabis \geq 1 day per week, and \geq 1 joint (~0.5 grams) per smoking day, during the 4 weeks prior to screening	Self-report during clinical interview
3. Urine test positive for recent cannabis use	Urine toxicology
4. Body Mass Index from 18.5-34 kg/m ²	Physical examination
5. Not currently seeking treatment for their cannabis use	Self-report during clinical interview
6. Able to perform all study procedures (i.e., does not experience discomfort or nausea from VR headset, can perform computer tasks)	Training session

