In each session, the participant will smoke two-thirds of one cannabis cigarette according to our paced-puff procedure (Foltin et al. 1987). They will complete an eye task battery (5 minutes per battery) 15 minutes prior to smoking as a baseline measure in each session, and again at the following timepoints: 0, 15, 30, 45, 60, 75, 90, 105, 120, and 165 minutes post-cannabis. Baseline assessments will be compared to those at post-cannabis timepoints.

In order to collect exploratory data, we will also conduct one pain assessment during the training session (described below).

Screening:

Initial telephone interviews will be carried out by research assistants who have been trained by [name], during which time potential participants will be asked about their current and past drug use and general health. To conduct this telephone interview, we are requesting a waiver of consent.

After initial determinations of eligibility over the phone, volunteers will come into the Cannabis Laboratory for two screening visits. At the first screening visit, they will be asked to sign our currently approved outpatient screening consent form (#7091R), allowing us to collect questionnaire data, conduct interviews, obtain medical information including a medical history and bloodwork (including blood pregnancy test for women at screening), and do an ECG. Potential participants will be told that they will be taking part in a study investigating the effects of smoked cannabis and eye movements. After the general screening process, a study psychologist ([name], [name], [name]) will explain the details of the study procedure and confirm that the volunteer understands what participation entails, after which they will sign the study-specific consent form (#7844).

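### The stated goal is an indicator of cannabis use or intoxication, but none of the named analyses measures how well the eye tests classify sessions as active or placebo

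*Combined protocol and SAP*

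**What the plan says.** The Lay Summary gives the purpose as examining the effect of 7% versus 0% THC on eye movements, "with the goal of defining the utility of the eyes as potential objective indicators of cannabis use and intoxication". It closes by saying that the findings may "characterize the validity of eye tests as an objective measure of cannabis use and intoxication". The paragraph on the state of the field, before the Specific Aims, says that the study seeks an objective and accurate measure of impairment. The formal aim is narrower: "Aim 1: Examine the relationship between cannabis intoxication and eye behavior".

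Four kinds of analysis are named:

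- **Own baseline.** The Lay Summary describes the eye battery "with the goal of comparing baseline values to the ten post-cannabis timepoints to detect changes in eye behavior as a function of cannabis intoxication". The General Overview under Study Procedures repeats it: "Baseline assessments will be compared to those at post-cannabis timepoints".
- **Placebo.** Hypothesis (a) under Aim 1 sets active against placebo cannabis, and the Lay Summary frames the effect the same way.
- **Correlation.** Eye outcomes are to be correlated with the visual analogue ratings (Lay Summary, Laboratory Sessions).
- **Latent pupil features.** Principal component and factor analysis are named in A Proposed Objective Ocular Approach.

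The supplied text has no statistical analysis section and gives no derivation of the sample size of 30.

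**The concern.** Utility, validity and accuracy as an indicator are properties of a test applied to individuals: how often it flags someone who has just smoked, and how often it flags someone who has not. The four named analyses describe group differences, associations and data structure. No sensitivity, specificity, AUC, study cut-off, decision rule or validation scheme appears. The protocol does cite such a measure for alcohol: about 88% correctly classified by horizontal gaze nystagmus (The Current Road-side Approach). It plans no counterpart for cannabis.

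Two things are at stake. First, a significant contrast could be reported as evidence of validity when the overlap between active and placebo readings is large. Second, the Lay Summary looks for a characteristic pattern across four tests. If a pattern is derived from 30 people and judged on the same people, its accuracy will be overstated.

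The own-baseline comparison has a further limit. A roadside test, the use that motivates the work, has no sober reading from the same person. That limit does not apply to the placebo contrast.

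**Working it through.** **Inputs.** From the documents: 30 participants and two sessions each, so at most 30 active and 30 placebo sessions, with ten post-smoking batteries per session. The documents give no alpha, power, effect size or correlation, so the figure of 30 cannot be reproduced. Assumed here: two-sided 5% test, 80% power, normal outcomes with equal variance, and within-person correlation r from 0.3 to 0.9.

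**Step 1: detectable paired effect.** By normal approximation, dz = (1.960 + 0.842)/√30 = 0.51. By the paired t-test, dz = 0.53. An observed dz of 2.045/√30 = 0.37 is just significant.

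**Step 2: what that means for classification.** For one feature and a single reading per session, d = dz × √(2(1 − r)), AUC = Φ(d/√2), and sensitivity at 95% specificity = Φ(d − 1.645). At the best cut-off, sensitivity = specificity = Φ(d/2).

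| dz | r | d | AUC | Sensitivity at 95% specificity | Sensitivity = specificity, best cut-off |
|---|---|---|---|---|---|
| 0.53 | 0.3 | 0.63 | 0.67 | 15% | 62% |
| 0.53 | 0.5 | 0.53 | 0.65 | 13% | 60% |
| 0.53 | 0.7 | 0.41 | 0.61 | 11% | 58% |
| 0.53 | 0.9 | 0.24 | 0.57 | 8% | 55% |
| 1.0 | 0.5 | 1.00 | 0.76 | 26% | 69% |

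Even when each person serves as their own comparator, dz = 0.53 means that only Φ(0.53) = 70% of individuals move in the expected direction.

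**Step 3: validating on the same people.** I simulated pure noise for 30 people, two sessions and ten batteries per session, with assumed variance shares of 0.4 for participant and 0.2 for session. The classifier was a linear discriminant, with 200 runs per feature count. The true AUC is 0.50.

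| Features | Apparent AUC | Cross-validated by battery | Cross-validated by participant |
|---|---|---|---|
| 8 | 0.60 | 0.56 | 0.49 |
| 20 | 0.67 | 0.60 | 0.50 |

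Only holding out whole participants removes the false signal.

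**Step 4: precision from 30 people.** The Wilson interval is [p + z²/2n ± z√(p(1 − p)/n + z²/4n²)]/(1 + z²/n). With p = 24/30 and z = 1.96 it is (0.864 ± 0.157)/1.128, or 63% to 90%. For 27/30 it is 74% to 97%. A half-width of 10 points at 80% would need 1.96² × 0.8 × 0.2/0.1² = 61.5, so 62 participants. The Hanley–McNeil 95% half-width for the AUC, treating 30 active and 30 placebo readings as independent, is 0.14 at AUC 0.6 and 0.11 at AUC 0.8.

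**The case against.** The strongest reply is that the trial does not promise a validated test. The indicators are described as potential, the validity sentence is governed by the word may, and Aim 1 only examines a relationship. The contrasts named do address that aim. This stands: the gap is between the wider goal and the analyses, and Aim 1 is not defeated.

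Three stronger readings are tempting, and the documents do not support them.

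- **That the plan only compares average changes from own baseline.** It does not. The 7% versus 0% comparison, the correlations and the latent-feature analyses are also named, and the text never says that eye outcomes will be compared as means. A group-level comparison is the natural reading, but it is an inference.
- **That the study commits itself to a predictive model.** The phrase occurs in a sentence about earlier work: "no published studies have used modern VR eye trackers and data analysis to build a predictive model of cannabis intoxication". It identifies a gap in the literature.
- **That the eye tests would miss most users.** The low sensitivities apply to one feature at the smallest reliably detected effect. They are not a forecast, and a pattern across four tests could do better.

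It is also fair to say that 30 people cannot settle utility. Participants are current users with positive urine tests, asked to abstain for 15 hours, with eye abnormalities excluded. Specificity among drivers in general cannot be estimated from them. This limits what the added analysis can claim but does not remove the need for it.

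**Conclusion.** The point holds as a mismatch between goal and analysis. No named analysis yields a measure of classification, so a significant result would support Aim 1 and leave utility and validity unaddressed. The numbers show why one cannot stand in for the other: an effect that 30 pairs would usually detect is compatible with an AUC of 0.57 to 0.67. That range rests on the assumed alpha, power, correlation and normal equal-variance model, and it describes one feature. The conclusion that the measure is missing depends on none of these. The limit lies in the stated analysis, since the blinded crossover already provides the data for a pilot-level estimate. This is an inexpensive improvement worth making; it is not grounds for calling the main aim unanswerable.

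**What to change.** Add one prespecified secondary analysis of discrimination between 7% and 0% sessions:

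- Name one post-smoking timepoint, or one fixed window, before unblinding.
- Fix a short list of features from the four tests.
- Use leave-one-participant-out cross-validation, holding out all of a person's batteries together and setting any cut-off in the training data.
- Report AUC with a bootstrap interval that resamples participants, and sensitivity at a specificity fixed in advance. With 30 placebo sessions, each one is worth 3.3 points of specificity, so the chosen level should be one that can be estimated.
- Make the version without own-baseline subtraction the main one, and give the version with it as a supplement.
- Base any utility or validity statement on this result. Label it pilot-level and limited to current cannabis users abstinent for about 15 hours.

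Keep the existing contrasts for Aim 1. No new data are needed. The cost is a modest amount of analysis and a result that will be less precise, and probably less favourable, than a significant contrast would suggest.
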